10. Vital Signs (blood pressure, heart rate, temperature, height, weight)
11. Methacholine challenge (not to be performed if results were obtained within the past year in the separate screening protocol)
12. Between visit 1 and 2 subjects will fill out diary cards weekly.

Visit 1 can be completed in multiple visits if they occur within the visit window.

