### **Between Visits 6 and 7 (Days 5 and 6)**

Subjects will complete the diary card daily

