
**Analysis of RV-induced lower-respiratory symptoms:** The lower respiratory symptom scores from challenge study-days 0, 1, 2, 3, 4, and 7, will be analyzed in two different ways. In the first approach; due to the expected infrequency of lower respiratory symptoms in the allergic rhinitis and healthy control cohorts, cumulative lower respiratory total symptom (CLRTS) will be computed for challenge period; day 0 to day 4, and for challenge period; day 0 to day 7. In the second approach the daily total lower respiratory symptom scores will be analyzed.

**Analytical approach #1:** We will use the total lower respiratory symptom scores of challenge days 0, 1, 2, 3, and 4 to compute to a cumulative lower respiratory symptom score (CLRTS) for challenge period day 0 to day 4, and we will use the total lower respiratory symptom scores of challenge days 0, 1, 2, 3, 4, and 7 to compute a CLRTS for challenge period day 0 to day 7. **Analytical approach:** The CLRTS will be analyzed as integer scaled random variables by way of a Negative Binomial (NB) generalized estimating equation (GEE) model. **GEE model specification:** The GEE model specification for the CLRTS analysis will include two predictor variables. One predictor variable will identify the study-group (i.e. asthmatics, allergic rhinitis controls, and healthy-controls) while the other predictor variable will identify the challenge period (i.e. day 0 to day 4, or day 0 to day 7). **Variance estimation:** An “unstructured” variance-covariance matrix form will be utilized to account for the inherent correlation between the first set of CLRTS scores (challenge day 0 to challenge day 4) and the second set of CLRTS scores (challenge day 0 to challenge day 7). **Hypothesis testing:** Wald tests will be conducted to determine if the means of CLRTS distributions for each challenge period differ from study-population to study populations. A Bonferroni two-sided  $p \leq 0.0167$  (0.05/3) criterion will be utilized as the null hypothesis rejection rule for the intra-challenge-period, between-group comparisons.

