**Analytical approach #2:** We will analyze the lower respiratory total symptom scores for challenge days 0, 1, 2, 3, 4, and 7 as repeated measures in this approach. **Analytical approach:** The lower respiratory total symptom score data will be analyzed by way of a negative-binomial generalized estimating equation (GEE) model. **Model specification:** The GEE model specification will include two predictor variables. One predictor variable will identify the study-group (i.e. asthmatics, allergic rhinitis controls, and healthy-controls), while the other predictor variable will identify the challenge study-day (i.e. day 0, 1, 2, 3, 4, or 7). **Variance estimation:** A “working independence” variance covariance matrix form will be utilized to account for the inherent *intra-subject* measurement correlation induced by the repeated measures aspect of the RV challenge study design. **Hypothesis testing:** Wald chi-square tests will be utilized to test if the means of total lower symptom score distributions on a particular challenge day differed between the 3 different study-groups. The primary focus will be to determine if the means of total lower symptom score distributions differed between the 3 different study-groups on study-days 3 and 4, when symptoms are expected to peak.

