***Analysis of circulating eosinophil count:*** Changes in the absolute eosinophil count (AEC) from day -7 to post-challenge day 4 will be compared between the 3 different groups via ANOVA. ***Model specification:*** The primary source of  $\Delta$  AEC variation that will be examined will be the variation due to study-group to study-group variation. ***Hypothesis testing:*** We will test if the 3 underlying study-population  $\Delta$  AEC distributions share the same mean. A  $p \leq 0.05$  decision rule will be utilized as the null hypothesis rejection rule for this test. If rejected a Bonferroni corrected two-sided  $p \leq 0.05/3$  decision rule will be utilized as the null hypothesis rejection rule for between-group comparisons. ***Alternative analytical approach:*** If the ANOVA model assumptions are violated, the  $\Delta$  %EC data will be analyzed by *distribution-free* permutation methods.

***Analysis of eosinophil percent of total cells:*** Changes in the eosinophil percent of total cells ( $\Delta$  %EC) from day -7 to post-challenge day 4 will be compared between the 3 different groups via ANOVA. ***Model specification:*** The primary source of  $\Delta$  %EC variation that will be examined will be the variation due to study-group to study-group variation. ***Hypothesis testing:*** We will test if the 3 underlying study-population  $\Delta$  %EC distributions share the same mean. A  $p \leq 0.05$  decision rule will be utilized as the null hypothesis rejection rule for this test. If rejected a Bonferroni corrected two-sided  $p \leq 0.05/3$  decision rule will be utilized as the null hypothesis rejection rule for between-group comparisons. ***Alternative analytical approach:*** If the ANOVA model assumptions are violated, the  $\Delta$  %EC data will be analyzed by *distribution-free* permutation methods.

***Analysis of upper respiratory symptom scores:*** The upper respiratory symptom scores that will be reported daily from challenge study day 0 to challenge study day 7, will be analyzed in two ways. In the first approach, cumulative upper respiratory total symptom (CURTS) will be computed for challenge days 0 to 4, and for challenge days 0 to 7. In the second approach the daily total upper respiratory symptom scores will be analyzed. *Please see the analytical plan for the analysis lower respiratory symptom scores for further details (section 13.4.2).*

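### The primary lower-respiratory-symptom analysis compares raw score levels with no baseline, so any pre-existing chest-symptom difference is counted as RV-induced; its day 0 to day 7 total also omits diary days 5 and 6

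*Combined protocol and SAP*

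**What the plan says.** Section 2.2 frames the objective as an increase caused by RV in one cohort but not in the other two, and the primary outcome is labelled RV-induced.

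Section 13.4.2 gives two analyses of the lower respiratory score.

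- **Approach #1** compares cumulative scores. For the shorter period: "We will use the total lower respiratory symptom scores of challenge days 0, 1, 2, 3, and 4 to compute" the total. For the longer period, ending on day 7, the plan takes "total lower respiratory symptom scores of challenge days 0, 1, 2, 3, 4, and 7 to compute a CLRTS for challenge period". On the model: "The GEE model specification for the CLRTS analysis will include two predictor variables". These are study group and challenge period. Cohort means are compared pairwise within each period at two-sided 0.05/3.
- **Approach #2** works by day: "We will analyze the lower respiratory total symptom scores for challenge days 0, 1, 2, 3, 4, and 7 as repeated measures in this approach". Day 0 is one more outcome day, and the main tests compare cohort means on days 3 and 4.

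Neither approach subtracts or adjusts for a pre-inoculation score. In sections 13.4.2 and 13.4.4, IL-25 and FEV1 are analysed as change from day 0 with day 0 also adjusted for.

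On the diary, section 8.2 says for the period before inoculation: "Between visit 1 and 2 subjects will fill out diary cards weekly". For days 5 and 6 it says: "Subjects will complete the diary card daily". Section 13.4.4 refers to "The upper respiratory symptom scores that will be reported daily from challenge study day 0 to challenge study day 7" and sends the reader back to the lower-symptom plan for the method.

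**The concern.** A between-cohort difference in level is not a difference in response to RV. The cohorts are not randomised, and the entry rules make them differ in airway disease. AR subjects must have a negative methacholine challenge, and no viral wheeze or inhaler use for 6 years. Asthmatics must be controlled, but may still have occasional cough, tightness or wheeze. Such a background adds to every scored day, and no term in either model removes it. Primary objective 2 could then be declared met partly or wholly on symptoms that were present before the virus was given.

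Separately, a total described as running from day 0 to day 7 omits two post-inoculation days on which the diary is completed. The group's earlier study (section 1.3) suggests that much of the asthma–control gap opened after day 4.

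**Working it through.** **1. The plan's own figure.** 0.05/3 = 0.0167, as stated. Section 13.7 gives no power or sample size for this endpoint.

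**2. Days scored.** Day 0 is 1 of 5 days (20%) in the shorter total and 1 of 6 (16.7%) in the longer. The longer total leaves out 2 of 8 calendar days (25%), or 2 of 7 post-inoculation days (28.6%).

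**3. What the documents allow for background.** No pre-inoculation lower score is given. Section 1.3 reports day 0–4 totals in infected subjects, and these include any background. If RV had contributed nothing, and the scoring was the same, the ceilings per day are:

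- low-IgE asthma: 1.0/5 = 0.20
- high-IgE asthma: 4.2/5 = 0.84
- control: 0.4/5 = 0.08

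**4. False-claim rate when RV does not act differently in the cohorts.** The simulation has 20 versus 20 subjects and 20,000 trials per setting. Subject effects are gamma and scores Poisson. The test is a robust Wald test of the log mean ratio of the day 0–4 total at 0.0167. Two assumptions about controls were used:

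- *A:* RV adds nothing in either cohort; controls have a 5-day mean of 0.4 (0.08 per day).
- *B:* controls have no background; RV adds 0.08 per day on days 1–4 in both cohorts.

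| Asthma background, points/day | A | B |
|---|---|---|
| no excess over controls | 1.4–2.4% | 1.0–1.4% |
| 0.05 | – | 8–9% |
| 0.1 | about 2–3.5% | 24–32% |
| 0.2 | 23–29% | 58–78% |

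Ranges are over the spread of the subject effects: gamma shape 0.3–2 in A (0.5 and 1.0 at 0.2 points/day), gamma variance 0.5–2 in B. A and B differ because the excess over controls drives the result. At 0.1 the excess is 0.1 − 0.08 = 0.02 per day in A and 0.10 in B.

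**5. Does a baseline cure it?** Under B, testing the days 1–4 total minus 4 × the day-0 score (Welch t) rejects in 0.8–2.9% of trials for backgrounds from 0 to 0.8. Dropping day 0 from the sum is not enough. At 0.1 per day the background falls only from 5 × 0.1 = 0.5 to 4 × 0.1 = 0.4 points.

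**6. Days 5 and 6.** Section 1.3 gives totals by day 21 of 13.5 (high IgE), 8.5 (low IgE) and 0.7 (control). Assume that the burden after day 4 was spread evenly over days 5–21, which is 17 days.

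| | Per day, days 5–21 | Full day 0–7 | As scored | Lost |
|---|---|---|---|---|
| High IgE | (13.5−4.2)/17 = 0.547 | 4.2+3×0.547 = 5.84 | 4.2+0.547 = 4.75 | 19% |
| Low IgE | (8.5−1.0)/17 = 0.441 | 1.0+3×0.441 = 2.32 | 1.0+0.441 = 1.44 | 38% |
| Control | (0.7−0.4)/17 = 0.018 | 0.4+3×0.018 = 0.45 | 0.4+0.018 = 0.42 | 8% |

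Proportionally more is lost in asthma, so the asthma–control ratio shrinks.

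**The case against.** **Entry rules limit background.** Asthmatics need an ACT score of at least 20. Beta-2-agonist use on 4 or more days in any week, or on 2 or more nights in the month, excludes. Asthma control is reviewed on day 0, and inoculation may be delayed. This stands, and the cohort should not be described as defined by chest symptoms. But none of these rules sets a lower-symptom score cutoff; the only score limit at inoculation is for the upper airway.

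**The earlier data do not look like flat background.** Low-IgE asthmatics averaged 0.20 points per day over days 0–4 and 0.44 over days 5–21. This also stands. A background of 0.2 is the most that the low-IgE figure permits, and larger assumed values treat nearly all of the infected score as background. Pooling the 10 low-IgE and 6 high-IgE subjects gives (10×1.0 + 6×4.2)/16 = 2.2, or 0.44 per day. Simulated rates at such values should not be read as an expectation.

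**Baseline information is not wholly absent.** Approach #2 would show a day-0 difference, and section 13.6 states a before/after null for every primary outcome. However, 13.4.2 specifies no such test for symptoms, and a within-cohort test would not correct the between-cohort one.

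**Precedent.** The earlier study also summed from day 0. That explains the convention but does not turn a level into a response.

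**Days 5 and 6 may matter little.** In the earlier study, high-IgE asthmatics already differed from controls by day 4 (P = .0003), and the day-21 totals do not isolate days 5 and 6. The omission also leaves the day 0–4 total untouched. All of this is fair; the loss in step 6 is only indicative.

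**Conclusion.** The primary symptom tests do not estimate what objective 2 asks. They would credit to RV any stable chest-symptom difference present before inoculation, and the plan has no safeguard whatever the true background is. This follows from the text alone.

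The size does not. With no excess background the error is near nominal. At 0.1 points per day it is about 2–32%, and at 0.2 about 23–78%, depending on the assumption for controls. These figures are illustrative.

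A reader might infer more than the documents support:

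- *That a false claim is likely.* This needs a pre-inoculation score, which the documents do not give.
- *That both faults favour the asthma hypothesis.* The missing baseline can inflate the contrast, while omitting days 5 and 6 probably shrinks it. They cannot be assumed to cancel.
- *That the Wald test is itself anti-conservative.* Simulated size under equal means ranges from about 0.8% to 3.9% with the assumed mean and dispersion, so no direction is established.
- *That the two-predictor models cannot support the tests.* Testing within each period or day implies cohort-by-time means. This is a matter of stating the interaction explicitly.

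**What to change.** 1. Take day 0 out of the outcome sum. Use the pre-inoculation day-0 lower respiratory score as baseline, adding the weekly pre-inoculation diary entries where available. State which entries count. Section 8.2 describes scores recorded twice daily but weekly cards between Visits 1 and 2, and a day-0 evening entry could follow inoculation.
2. Make the primary between-cohort test a baseline-adjusted contrast, chosen in advance. One option is the change in mean daily score from baseline to days 1–4 and to days 1–7. The other is the negative binomial GEE with day 0 as the pre-period and the group-by-pre/post interaction as the test. Add a permutation p-value as a check. The two options measure different things (points versus ratios), and the log-link interaction cannot be estimated if a cohort has no day-0 symptoms at all.
3. Include diary days 5 and 6 in the day 1–7 score.
4. Apply the same changes to the upper respiratory scores in section 13.4.4.

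The cost is plan wording and programming; the day-0 and day 5–6 entries are already collected. The downside is some loss of precision. With a 5 to 28 day interval between Visits 1 and 2, weekly cards may yield only about 1 to 4 entries, so the baseline may be noisy. With no power stated for this endpoint, that loss cannot be set against a target.

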### 13.4.3 Supportive Analyses of the Primary Outcome(s)

***Supportive analyses for the primary outcomes:*** As supportive analyses we will examine the IL-25 cytokine expression in the nasal washes collected on study days 1, 2, 3, 4, and 7 of the RV 16 challenge. These data will be analyzed in exactly the same way as the nasal scraping derived IL-25 expression data (see above).

### 13.4.4 Analyses of Secondary and Other Outcome(s)

As indicated in section 3.1 and 13.2 there will be several secondary outcome variables and the analytical plans related to these outcome variables will be briefly described in this subsection.

***Analysis of expression of nasal epithelial cells of a type 2 cytokine-inducing profile:*** We will evaluate the time course of IL-33 and TSLP transcription expression by qPCR on nasal sample obtained on challenge days 0, 1, 2, 3, 4, and 7. ***Endpoint transformations:*** Since we expect that the IL-33 and TSLP expression measurements on any particular challenge day (i.e. day 0, 1, 2, 3, 4, and 7) will be distributed approximately Log-Normal (positive skewed distribution), we will transform the IL-33 and TSLP expression data to the natural logarithmic scale. ***Units of analysis:*** The day 0  $\log_e$ (cytokine qPCR expression) measurements will be subtracted from the post-challenge day 1, 2, 3, 4, and 7  $\log_e$ (cytokine qPCR expression) measurements and these *subject-specific* pre-versus post-challenge changes in  $\log_e$ (cytokine qPCR expression) will be the units of analysis. ***Analytical approach:*** The changes in  $\log_e$ (IL-33 qPCR expression) on post-challenge days 1, 2, 3, 4, and 7, and the changes in  $\log_e$ (TSLP qPCR expression) on post-challenge days 1, 2, 3, 4, and 7, will be analyzed as repeated measures by way of linear mixed models (LMM). ***Model specification:*** Per outcome variable, the LMM specification will be the same as the LMM specification for the analysis of the post-challenge days 1, 2, 3, 4, and 7 changes in  $\log_e$ (IL-25 qPCR expression) (see section 13.4.2 above). ***Hypothesis testing:*** The *between-group* hypothesis, and the *within-group* hypotheses, will be identical to those described in “Hypothesis testing” section of the IL-25 qPCR analytical approach (see section 13.4.2 above).

***Analysis of IL-25, IL-33 and TSLP protein expression by EIA.*** We will evaluate the time course of IL-25, IL-33 and TSLP protein expression by EIA on nasal sample obtained via immunosorbent sponge on challenge days 0, 1, 2, 3, 4, and 7. ***Analytical approach:*** IL-25, IL-33 and TSLP protein expression data will be analyzed as repeated measures via linear mixed models in exactly the same way as the IL-25, IL-33 and TSLP qPCR expression data (see sections 13.4.2 and immediately above).

***Analysis of albuterol metered dose inhaler utilization:*** Albuterol metered dose inhaler utilization will be evaluated on challenge days 0, 1, 2, 3, 4, and 7 within the asthma cohort to determine if the frequency of albuterol inhaler utilization is related to severity of symptoms.

**Analytical approach:** Based on diary records, the total number of times that the subjects used their albuterol metered dose inhaler will be determined for study days 0, 1, 2, 3, 4, and 7, and these frequencies will be analyzed via a Negative Binomial generalized estimating equation (GEE) model. **Hypothesis testing:** Our primary interest, will be to compare albuterol metered dose inhaler utilization on post-challenge days 3 and 4 when lower and upper respiratory symptoms are expected to peak to challenge days 0, 1, 2, and 7. The Wald test will be the pivotal quantity for the *inter-day* comparisons and the multiple comparison experimental type 1 error rate for the inter-day comparisons will 0.05.

**Secondary analyses:** As secondary analyses, Negative Binomial GEE regression models will be utilized to determine if RV loads and total upper and lower respiratory symptoms scores on challenge days 0, 1, 2, 3, 4, and 7 predict albuterol metered dose inhaler utilization on challenge days 0, 1, 2, 3, 4, and 7.

**Analysis of FEV1:** Measurements of FEV1 will be acquired on challenge study days: 0, 1, 2, 3, 4, and 7. **Data transformation:** If the FEV1 measurement distributions for challenge study days 0, 1, 2, 3, 4, and 7 are positively skewed, the FEV1 will be transformed to the natural logarithmic scale, otherwise the FEV1 data will be analyzed on the mL scale. **Units of analysis:** The challenge study day 0 FEV1 measurements will subtracted from the post-challenge FEV1 measurements of challenge study days 1, 2, 3, 4, and 7 and these *subject-specific* pre- versus post-challenge changes in FEV1 will be the units of analysis. **Analytical approach:** The post-challenge changes in FEV1 will be analyzed via a LMM. **LMM specification:** Two source of variability in the post-challenge changes in the FEV1 measurements will be examined. One source of variability will be the study-group to study group variability (i.e. asthmatics, allergic rhinitis controls, and healthy-controls), while the other source of variation will be the post-challenge day to day variability (i.e. challenge study day 1, 2, 3, 4, or 7). Variability in the FEV1 changes due to inherent differences in the challenge study day 0 Fev1 (baseline) will be extracted from the residual error to increase statistical power. **Random effects:** *Subject-specific* and *time-specific* random effects will be incorporated into the LMM to allow *intra-subject* measurement correlation to be accounted for in variance estimation and hypothesis testing. **Hypothesis testing:** The pivotal *between-group* comparisons will be focused on the post-challenge day 3 and day 4 changes in FEV1 when symptoms are expected to peak. Baseline adjusted post-challenge day 3 and day 4 mean changes in FEV1 will be compared in a pairwise manner between the 3 different study populations. In order to maintain an *intraday specific* experimental type I error rate 0.05, a Bonferroni corrected two-sided  $p \leq 0.05/3$  decision rule will be utilized as the null hypothesis rejection rule. Post-challenge day 1, 2 and 7 *between-group* comparisons of the changes in FEV1 will be consider as secondary comparisons, and the same hypothesis testing procedures will be employed to conduct these *between-group* comparisons. *Within-group* related hypotheses will also be considered as secondary hypotheses.

**Analysis of FeNO:** FeNO will be derived from lung-function tests that will be conducted on challenge study days 0, 1, 2, 3, 4, and 7. **Data transformation:** If the FeNO measurement distributions for challenge study days 0, 1, 2, 3, 4, and 7 are positively skewed, the FeNO data will be transformed to the natural logarithmic scale, otherwise the FeNO data will be analyzed on the ppb scale. **Analytical approach:** The FeNO data will be analyzed via a LMM. **LMM specification:** The LMM specification will an exactly the same as the LMM model specification for the FEV1 analysis (see above). **Hypothesis testing:** The pivotal *between-group* comparisons will be focused on the post-challenge day 3 and day 4 changes in FeNO when symptoms are expected to peak. Baseline adjusted post-challenge day 3 and day 4 mean changes in FeNO will be compared in a pairwise manner between the 3 different study-populations.

In order to maintain an *intraday specific* experimental type I error rate 0.05, a Bonferroni corrected two-sided  $p \leq 0.05/3$  decision rule will be utilized as the null hypothesis rejection rule for this set of tests. Post-challenge day 1, 2, and 7 *between-group* comparisons of the changes in FeNO will be considered as secondary comparisons, and the same hypothesis testing procedures will be employed to conduct these *between-group* comparisons. *Within-group* related hypotheses will also be considered as secondary hypotheses.

***Analysis of bronchial hyperreactivity (methacholine PD20):*** The changes in bronchial hyperactivity from before challenge to after challenge will be quantified in terms of the changes in methacholine challenge PD20 from pre-challenge day -7 to post challenge day 4 ( $\Delta$  PD20). ***Analytical approach:*** The  $\Delta$  PD20 data will be analyzed by way of analysis of variance (ANOVA). ***Model specification:*** The primary source of  $\Delta$  PD20 variation that will be examined will be the variation due to study-group to study-group variation. ***Hypothesis testing:*** We will test if the 3 underlying study-population  $\Delta$  PD20 distributions share the same mean. If rejected a Bonferroni corrected two-sided  $p \leq 0.05/3$  decision rule will be utilized as the null hypothesis rejection rule for between-group comparisons. ***Alternative analytical approach:*** If the ANOVA model assumptions are violated, the  $\Delta$  PD20 data will be analyzed by *distribution-free* permutation methods.

***Analysis of circulating eosinophil count:*** Changes in the absolute eosinophil count (AEC) from day -7 to post-challenge day 4 will be compared between the 3 different groups via ANOVA. ***Model specification:*** The primary source of  $\Delta$  AEC variation that will be examined will be the variation due to study-group to study-group variation. ***Hypothesis testing:*** We will test if the 3 underlying study-population  $\Delta$  AEC distributions share the same mean. A  $p \leq 0.05$  decision rule will be utilized as the null hypothesis rejection rule for this test. If rejected a Bonferroni corrected two-sided  $p \leq 0.05/3$  decision rule will be utilized as the null hypothesis rejection rule for between-group comparisons. ***Alternative analytical approach:*** If the ANOVA model assumptions are violated, the  $\Delta$  %EC data will be analyzed by *distribution-free* permutation methods.

***Analysis of eosinophil percent of total cells:*** Changes in the eosinophil percent of total cells ( $\Delta$  %EC) from day -7 to post-challenge day 4 will be compared between the 3 different groups via ANOVA. ***Model specification:*** The primary source of  $\Delta$  %EC variation that will be examined will be the variation due to study-group to study-group variation. ***Hypothesis testing:*** We will test if the 3 underlying study-population  $\Delta$  %EC distributions share the same mean. A  $p \leq 0.05$  decision rule will be utilized as the null hypothesis rejection rule for this test. If rejected a Bonferroni corrected two-sided  $p \leq 0.05/3$  decision rule will be utilized as the null hypothesis rejection rule for between-group comparisons. ***Alternative analytical approach:*** If the ANOVA model assumptions are violated, the  $\Delta$  %EC data will be analyzed by *distribution-free* permutation methods.

***Analysis of upper respiratory symptom scores:*** The upper respiratory symptom scores that will be reported daily from challenge study day 0 to challenge study day 7, will be analyzed in two ways. In the first approach, cumulative upper respiratory total symptom (CURTS) will be computed for challenge days 0 to 4, and for challenge days 0 to 7. In the second approach the daily total upper respiratory symptom scores will be analyzed. *Please see the analytical plan for the analysis lower respiratory symptom scores for further details (section 13.4.2).*

***Analysis of innate immune deviating activity:*** IFN- $\alpha$ ,  $\beta$ ,  $\lambda$  and IL-15 data will be derived via qPCR from the RV challenge study day 0, 1, 2, 3, 4 and 7 nasal secretion samples. ***Data transformation:*** We expect that anti-viral

immunity expression data will be positively skewed, and therefore the expression data will have to be analyzed on the logarithmic scale. ***Units of analysis:*** Per endpoint (e.g. IFN- $\alpha$ ), the challenge study day 0  $\log_e(\text{expression})$  levels of the endpoint will be subtracted from the day 1, 2, 3, 4, and 7 post-challenge  $\log_e(\text{expression})$  levels of the endpoint and these *subject-specific* pre- versus post-challenge changes in  $\log_e(\text{expression})$  will be the units of analysis. ***Analytical approach:*** The logarithmic transformed expression data of each anti-viral immunity endpoint (e.g. IFN- $\alpha$ ) will be analyzed via a LMM. ***LMM specification:*** Two source of variability in the post-challenge changes in  $\log_e(\text{expression})$  will be examined. One source of variability will be the study-group (i.e. asthmatics, allergic rhinitis controls, and healthy-controls), while the other source will be the post-challenge day (i.e. challenge study days 1, 2, 3, 4, or 7). Variability in the post-challenge changes in  $\log_e(\text{expression})$  of the endpoint due to inherent differences in the  $\log_e(\text{expression})$  of the endpoint on challenge study day 0 (baseline) will be extracted from the residual error to increase statistical power. ***Random effects:*** *Subject-specific* and *time-specific* random effects will be incorporated into the LMM to allow *intra-subject* measurement correlation to be accounted for in variance estimation and hypothesis testing. ***Hypothesis testing:*** The pivotal *between-group* comparisons will be focused on the post-challenge day 3 and day 4 changes in  $\log_e(\text{expression})$  when peak symptoms are expected to occur. Baseline (i.e. challenge study day 0) adjusted day 3 and day 4 mean changes in  $\log_e(\text{expression})$  will be compared in a pairwise manner between the 3 different study-groups. In order to maintain an *intraday* experimental type I error rate 0.05, a Bonferroni corrected two-sided  $p \leq 0.05/3$  decision rule will be utilized as the null hypothesis rejection rule. Post-challenge day 1, 2, and 7 *between-group* comparisons of the changes in  $\log_e(\text{expression})$  will be considered as secondary comparisons, and the same hypothesis testing procedures will be employed to conduct these *between-group* comparisons. *Within-group* related hypotheses will also be considered as secondary hypotheses. ***Scale of interpretation:*** The point estimates and 95% confidence interval limits for the *between-group* and the *within-group* comparisons of mean  $\log_e(\text{expression})$  will be exponentiated so that the *between-group* comparisons and the *within-group* comparisons of the anti-viral immunity expression can be interpreted as a ratio of geometric means.

**Analysis of nasal biopsy samples:** Post-challenge day 4 nasal biopsy samples will be evaluated for % of infected cells and amongst the cells whether they display evidence of apoptosis (annexin V positive) or necrosis (PI positive). ***Analytic approach:*** Since the underlying distributions of these cell characteristics are complicated, we will use *distribution-free* permutation tests to conduct the *between-group* comparisons. ***Hypothesis testing:*** Based on the pseudo permutation test null distribution, a Bonferroni corrected two-sided  $p \leq 0.05/3$  decision rule will be utilized as the null hypothesis rejection rule for the *between-group* comparisons.

***Bivariate correlation analyses:*** As secondary analyses, we intend to examine bivariate relationships between several of the outcome variables. As one example, we intend to examine bivariate relationships between post-challenge day 0 to day 4 cumulative RV load and post-challenge day 3 and post-challenge day 4 expression of Th2 immune deviating activity (IL-25, IL-33 and TSLP). As a second example, we intend to examine bivariate relationships between post-challenge day 0 to day 4 post challenge cumulative RV load and post-challenge day 1, 2, 3, and day 4 innate expression of anti-immunity (IFN- $\alpha$ ,  $\beta$ ,  $\lambda$  and IL-15). Bivariate associations will be quantitatively expressed in terms of the non-parametric Spearman Rank correlation coefficient. Since multiple hypotheses will be tested, Bonferroni type I error rate corrections will be implemented in establishing the null hypothesis rejection rules.

